3.3 Recruitment Process

Participants enrolled in the MEND study have documented consent approving contact regarding participation in future studies for which MEND will be the baseline. We will recruit patients who have already undergone a CKD-MEND visit. CKD-MEND is a study of muscle mitochondrial energetics and dysfunction recruiting from the SKS and clinics. A comprehensive battery of testing including MRS/OS is performed. Data from the CKD-MEND visit performed within 180 days of entry into the current study will be used as baseline information.

3.4 Co-Enrollment Guidelines

Study participants will not be allowed to enroll in other clinical trials, as the effect of glutamine on this population is not clear.

3.5 Participant Retention

Every effort to retain enrolled participants will be made throughout the duration of the study in order to reduce bias related to loss to follow-up. Strategies for participant retention include:

- Thorough explanation of the importance of all 2 study treatment groups to the overall success of the study
- Detailed explanation of the study visit schedule and procedural requirements during the informed consent process, with re-emphasis at the end of each study visit
- Use of appropriate and timely visit reminder mechanisms. This includes weekly
 phone calls to assess participant adherence to regimen and remind participants of
 subsequent follow up visits
- Compensating participants for their time and effort in the study
- Immediate and multifaceted follow-up on missed visits

3.6 Participant Withdrawal

Participants will be allowed to voluntarily withdraw from the study for any reason and at any time. The investigator may withdraw participants from the study in order to protect their safety or if they are unwilling or unable to comply with required study procedures after consultation with the study sponsors and co-sponsors. Participants also may be withdrawn if the study sponsor, government or regulatory authorities, or site IRBs/ECs terminate the study before the planned end date. Reasons for withdrawal from the study will be recorded and a final evaluation will be made if feasible.

Participants who discontinue treatment but remain in the study will continue to be followed-up whenever possible.

4.0 STUDY TREATMENT/PRODUCT/INTERVENTION

4.1 Treatment/Product/Intervention Regimen(s)

- Active treatment will consist of 0.4 g/kg/day of L-glutamine (Nutrestore, EMMAUS Life Sciences, Inc Torrance, CA) in three divided daily doses. This dose was chosen based on a review of studies in the literature evaluating blood absorption of oral glutamine,³ biological activity of glutamine on immune function and modulation of muscle turnover.
- Placebo will consist of identical appearing maltodextrin powder.

4.2 Treatment/Product/Intervention Supply and Accountability

The Investigational Drug Pharmacy pharmacist must maintain complete records of all study drugs/products received from the Clinical Research Products Management Center and drug manufacturer and subsequently dispensed to study participants. All unused supplies must be returned to the Clinical Research Products Management Center after the study is completed or terminated.

4.3 Adherence Assessment

Adherence to the study treatment will be assessed by study coordinator phone call at day 7 of the study to assess adherence and inventory method to assess remaining medication/placebo at the end of the study. Adherence will be defined as consumption of at least 75% of the prescribed regimen. Up to 30 participants may be recruited to compensate for non-adherence or drop-out with the goal of 10 individuals completing in each treatment arm.

4.4 Toxicity Management

Currently, the mechanism whereby glutamine may cause harm or toxicity is unknown. There have been studies demonstrating increased levels of blood urea in those treated with glutamine. In the event of moderate or serious adverse effects (as defined in section 6.2) requiring treatment for such conditions as nausea, vomiting, confusion or bleeding thought to be related to toxicity from the study drug, the patient will be withdrawn from the study and adverse events reported.

Mild adverse events that do not requiring treatment and are thought to be potentially related to toxicity from the drug will prompt a 50% dose reduction.

4.5 Clinical Management of Pregnancy

All female participants of childbearing age who are sexually active will be asked to use contraception during the duration of the study and for 1 month afterwards as the effects of glutamine on fetal development are not clear.

Any females who become pregnant during the study period will stop taking the study product, but will continue with study procedures with the exception of the MRS/OS procedures. This is because the risks of ischemia in pregnancy are not known.

4.6 Concomitant Medications

Enrolled study participants may continue use of all concomitant medications — except those listed under criteria for exclusion or treatment discontinuation — during this study.

All concomitant medications taken or received by participants within the 4 weeks prior to study enrollment will be reported on applicable study case report forms. In addition to prescribed and over-the-counter medications (vitamins, herbal remedies, and other traditional preparations) will be recorded. Alcohol and recreational or street drug use will be recorded in clinical progress notes if needed for interpretation/documentation of observed participant health status. Medications used for the treatment of AEs that occur during study participation also will be recorded on applicable study case report forms.

5.0 STUDY PROCEDURES

Schedule of visits and procedures

An overview of the study visit and procedures schedule is presented in table 1. Presented below is additional information on visit-specific study procedures. Detailed instructions to guide and standardize all study procedures will be provided in the study-specific procedures manual.

Screening visit

Some components of the initial screening visit may be performed by telephone or in combination with other study visits in order to best accommodate participants' schedules. Once informed consent is obtained, the subject will undergo a baseline screening evaluation including an assessment of demographics, smoking history, medical history, medication inventory, with physical examination by study personnel. If the subjects meet the eligibility criteria the PI or Co-I will contact the subjects' primary physician regarding the subjects' involvement in the trial. The first study visit will be scheduled within 28 days of the screening visit. We will link to laboratory data from the CKD-MEND visit. The only lab tests that are not collected in CKD-MEND needed for this trial are metabolomics and redox proteome testing (see below).

Study drug dispensed at Visits 1 and 2

The participant will receive either placebo (maltodextrin powder) or glutamine from the Investigational Drug Service (IDS) and instructed on how to appropriately prepare it. He or she will be instructed to take the medication daily starting on the day after the study visit. They will be instructed to consume no protein for 30 minutes after glutamine or placebo consumption to prevent competitive binding for absorption with other amino acids.

Visit 1 – Visit 3

The participant will have been required to fast for 8 hrs prior to each visit and abstain from caffeine or smoking which can effect endothelial function for 8 hours prior to the visit. The following data will be obtained:

- vital signs,
- fasting blood collection,
- anthropometrics (height and weight),
- a urine pregnancy test will be given to women of child-bearing potential
- The MRS/OS and Muscle Fatigue tests will occur at the diagnostic imaging center at UWMC at visits 2 and 3. We will use the results of the MEND MRS/OS as the baseline for this study. Only 2 MRS/OS and Muscle Fatigue tests will be obtained per patient during this study because it will be assumed that there will be no carry-over effect of glutamine after the 3-week washout period.

Note: We may ask the subject to repeat the MRS/OS and Muscle Fatigue tests if more than 180 days has passed, or if they have had a change in health status, since their MEND visit.

Procedures:

An overview of the study visit and procedures schedule is presented in Appendix I. Presented below is additional information on visit-specific study procedures. Detailed instructions to guide and standardize all study procedures across sites will be provided in the study-specific procedures manual.

Blood testing for metabolic response profile (oxidative stress, inflammation, and plasma amino acids, metabolites, and electrolytes). Oxidative Stress and Inflammatory Biomarkers include: C-reactive protein and IL-6 levels will be determined using the automated Abbott FLX C-Reactive Protein Assay and by ELISA, respectively. Plasma F2-isoprostanes and isofurans will be measured by GC-MS as described by Roberts and Morrow at Vanderbilt University; Plasma Amino Acids, Metabolites and Electrolytes include: Plasma amino acid concentrations will be determined by reversed-phase HPLC after derivatization with phenylisothiocyanate.

- Plasma samples will be sent to Emory University for liquid chromatography high-resolution mass spectrometry (LC-MS) for untargeted metabolomics analysis.
- Clinical laboratory assays for determination of comprehensive metabolic panel (electrolytes, blood urea nitrogen, creatinine, glucose, albumin, total protein, calcium, alkaline phosphatase, ALT, AST, total bilirubin), CPK, lactate, triglyceride and ammonia levels will be performed at the *KRI Core Research laboratory*.
- -Testing the redox metabolome. Glutathione (GSH/GSSG) redox and cysteine (Cys/CySS) redox systems are oxidized in association with oxidative stress and in association with cardiovascular disease. Extracellar Cys/CySS redox state has been associated with events of early atherosclerosis, specifically monocyte adhesion to the endothelium and activation of the inflammatory cascade. Furthermore the redox state of the mitochondria represents a unique pool providing potential insight into the oxidative damage eventually contributing to necrosis and apoptosis. Plasma samples for all these

assays will be processed and sent to Emory University in Atlanta for analysis of mitochondrial redox control via systems of glutathione and thioredoxin models.

24 hour urine collection for urea nitrogen: Assessment of protein turnover will be performed using a timed 24hr urine collection for assessment of urine urea nitrogen. In order to confirm adequate collection and estimate muscle mass, we will also collect urine creatinine. Specimens less than 1liter in volume will be repeated.

Magnetic Resonance Spectroscopy and Optical Spectroscopy: As mentioned above, only 2 MRS/OS will be obtained as part of this study (Visit 2 and 3). The baseline MRS/OS will be obtained from the MEND study.

MRS/OS will be used to measure mitochondrial energy coupling (P/O), phosphorlylation capacity (ATP_{max}) and oxidative capacity (O_{2max}) of the first dorsal interosseus (FDI) skeletal muscle.⁴ The selection of the FDI skeletal muscle is based on the observation of higher oxidative type II muscle fiber content and degree of coupling similar in extent to the vastus lateralis commonly used to study of mitochondrial dysfunction. ^{5,6} As part of this procedure, two functional tests will be performed: an exercise protocol to help determine ATP_{max} and a resting (ischemia) protocol to determine mitochondrial energy coupling and the maximal rate of mitochondrial O_2 uptake (O_{2max}). Optical spectroscopy measuring the delay in Hemoglobin saturation relative to Myoglobin saturation after the onset of reperfusion will provide an index of vascular function. These functional tests assist to perturb the cell physiological state in order to measure the contents and dynamics of key metabolic compounds important in mitochondrial energy flux. ³¹P MRS is reliable with a documented coefficient of variation for oxidative phosphorylation of 5.1% and has a strong correlation with V_{O2max} .

Muscle Fatigue: We will test muscle fatigability at each follow-up visit. We will test the FDI muscle and determine the isometric force generated at 70% of maximal voluntary contraction (MVC) against a force transducer. Using labview software to measure and record the force-time waveform of each contraction we will initiate the protocol at 50 contractions per minute at 70% MVC for one minute. At each 1 minute increment will increase the contraction rate by 10 contractions per minute and reassess the subjects relative perceived exertion on a scale of 1-10 until the patient can no longer maintain the contraction waveform.

Vitals and measurements

Day 7 and 45 phone call:

All subjects will receive a phone call by study coordinators to confirm patients are taking their treatment/placebo medication in order to ensure adherence. They will also receive reminder of their subsequent follow up visits.

Visit 2 (day 15):

At visit 2 the participant will be questioned regarding any concerning symptoms noted during the treatment period. Adherence with the treatment or placebo will be confirmed by evaluating the quantity of remaining placebo or glutamine in the dispensed containers. Repeat fasting blood collection. They will also receive a repeat MRS/OS.

Washout (Day 16-37):

After the second visit, the participant will undergo a 3 week washout period prior to initiating the second treatment or placebo for another 2 week period.

Day 38:

The participant will cross-over to the opposite placebo or glutamine therapy for a two week course. We will phone the subject to remind them to begin taking the treatment/placebo.

Visit 3 (Day 53- Final visit):

During visit 3 the participant will be questioned regarding any concerning symptoms noted during the treatment period during visit 3. Adherence with the treatment or placebo will be confirmed by evaluating the quantity of remaining placebo or glutamine in the dispensed containers. Repeat testing will be performed to assess change during period 2 of the study. Fasting blood will be collected. They will also receive a repeat MRS/OS.

Table 1. Table of study treatments and procedures

Treatments/Procedures	Day -90 to 0 (Screening)	Day - 1 (Visit 1)	Day 0 - 14	Day 15 (Visit 2)	Day 16-37 Washout	Day 38	Day 39-52	Day 53 (Visit 3)
Visit may take this much time:	1 hour	3 hour		3 hour		(phone call)		3 hour
Informed Consent	Х							
Inclusion/Exclusion	X							
Medical History	Х							
Medication List	Х							
Demographics	Х					2.		
Brief Physical Exam	Х					Begin Study Product for Period 2.		
Pregnancy test*		X						
Vitals		Χ		Х				Х
Fasting Blood Draw		Χ		Х				Х
24hr urine collection				Х		study		Х
MRS/OS**				Х		gin S		Х
Muscle fatigue				Х		Be		Х
Study Product Dispensed		Χ		Х				
Study Product collected				Х				Х
Study Product Adherence				Х				Х
Phone Call to Participant			Day 7				Day 45	

^{*}Pregnancy test performed on females of childbearing age who are sexually active.

** MRS/OS and Muscle Fatigue for baseline is already done as part of CKD-MEND visit (within 180 days). If more than 180 days has passed, or if subjects have had a change in health status, these tests will be repeated at Visit 1.

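### Section 5 tells participants to start product the day after Visit 2, which falls on Day 16, the first day of the washout and not the Day 38 start

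*Combined protocol and SAP*

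**What the plan says.** Section 5.0, in the paragraph headed Study drug dispensed at Visits 1 and 2, gives a single start instruction: "He or she will be instructed to take the medication daily starting on the day after the study visit". It makes no exception for Visit 2.

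Later in Section 5.0, Visit 2 is placed on Day 15 and the washout on Days 16-37: "After the second visit, the participant will undergo a 3 week washout period prior to initiating the second treatment or placebo". The Day 38 entry reads "The participant will cross-over to the opposite placebo or glutamine therapy for a two week course", followed by "We will phone the subject to remind them to begin taking the treatment/placebo". Table 1 agrees. It shows product dispensed at Visits 1 and 2 only, a Day 16-37 washout column, and the start of period 2 product in the Day 38 column. Sections 2.3 and 7.6.1 also specify a 3-week washout.

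On adherence, Section 5.0 plans calls at Days 7 and 45 ("All subjects will receive a phone call by study coordinators to confirm patients are taking their treatment/placebo medication in order to ensure adherence") and a container check at Visits 2 and 3 ("Adherence with the treatment or placebo will be confirmed by evaluating the quantity of remaining placebo or glutamine in the dispensed containers"). Section 3.5 adds "Detailed explanation of the study visit schedule and procedural requirements during the informed consent process, with re-emphasis at the end of each study visit" and, weekly, "phone calls to assess participant adherence to regimen". Section 4.3 defines adherence as taking at least 75% of the regimen and allows up to 30 to be recruited to cover non-adherence and drop-out.

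**The concern.** The two instructions cannot both be followed for product handed out at Visit 2. The participant has that product from Day 15. The sentence in question is the only one in the documents that says what participants are told about when to start after dispensing, and no supplied text tells them to hold the Visit 2 supply until Day 38.

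What is at stake is exposure at Visit 3, not carryover. A participant in the placebo-then-glutamine sequence who starts on Day 16 may finish the glutamine well before Day 53. The primary MRS/OS would then be measured off treatment, as would the Visit 3 blood and 24-hour urine measures. That pulls the estimated effect toward zero. In the glutamine-then-placebo sequence an early start brings forward only placebo, so that sequence's contrast is not affected.

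**Working it through.** **1. Start days.** Rule: start day = visit day + 1.

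- Visit 1: -1 + 1 = Day 0. This agrees with the Day 0-14 column of Table 1.
- Visit 2: 15 + 1 = Day 16. The plan states Day 38 (last washout day 37 + 1), so the sentence is 38 - 16 = 22 days early.

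**2. Time off product at Visit 3 (Day 53).** The quantity dispensed at Visit 2 is not stated, so supply length L is an assumption. With daily use from Day 16, the last dose is on Day 15 + L, and days off = 53 - (15 + L).

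| Supply L (days) | Last dose | Days off at Visit 3 |
|---|---|---|
| 14 | Day 29 | 24 |
| 21 | Day 36 | 17 |
| 28 | Day 43 | 10 |
| 37 | Day 52 | 1 |

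**3. Carryover from period 1.** The last period 1 dose falls on Day 14-15, so it is 38-39 days before Visit 3 whether or not period 2 starts early. Carryover at Visit 3 is unchanged.

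**4. The plan's power figure.** Inputs from Section 7.3: 20 patients (10 per sequence), within-patient SD 0.375, difference 20% of 2.5 = 0.5, one-sided 0.05. Section 7.6.1 compares the sequences on the within-patient period differences, taken here as a two-sample t test with 18 df. The SD of a period difference is 0.375 × √2 = 0.530. The treatment estimate is half the difference between the sequence means, so its standard error is 0.5 × 0.530 × √(1/10 + 1/10) = 0.119. The noncentrality is 0.5 / 0.119 ≈ 4.2, and noncentral t power is 0.992. This agrees with the plan's statement of over 90%.

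**5. Effect of early starters.** Let k of the 10 placebo-then-glutamine participants start early undetected, with a fraction r of the effect left at Visit 3. Both k and r are assumptions. Only one sequence is affected and it carries half the weight, so

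expected estimate = 0.5 - 0.25 × (k/10) × (1 - r).

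For k = 3, r = 0: 0.5 - 0.25 × 0.3 = 0.425. Power is from 400,000 simulated trials per row.

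| k of 10 | r | Expected estimate | Power |
|---|---|---|---|
| 0 | – | 0.500 | 0.992 |
| 1 | 0 | 0.475 | 0.985 |
| 3 | 0 | 0.425 | 0.956 |
| 5 | 0 | 0.375 | 0.902 |
| 10 | 0 | 0.250 | 0.650 |
| 3 | 0.5 | 0.4625 | 0.982 |
| 5 | 0.5 | 0.4375 | 0.969 |
| 10 | 0.5 | 0.375 | 0.919 |

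Noncentral t gives 0.649 at a difference of 0.25, in agreement with the k = 10, r = 0 row.

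**6. If early starters are detected.** Excluded without replacement, the expected estimate stays at 0.50 and power is 0.989 (k = 1), 0.977 (k = 3) or 0.947 (k = 5). Full replacement under Section 4.3 restores 0.992.

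**7. Detection alone does not restore period 2.** Suppose a weekly call on Day 22 stops an early start. Days 16-21 use 6 of 14 days' product, leaving 8. Resumed on Day 38 or 39, these run out on Day 45 or 46, which is 8 or 7 days before Visit 3. Table 1 shows no dispensing after Visit 2, and no resupply is stated.

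**The case against.** The strongest reply is that nobody reading Section 5 as a whole would dose on Day 16. The sentence is general handling text, written with Visit 1 in mind. The dated entries that follow it, Table 1 and Sections 2.3 and 7.6.1 all give the washout. Section 3.5 has the schedule repeated at the end of every visit, including Visit 2 when the product is handed over. The Day 38 call prompts the start, and at Day 45 someone who finished on Day 29 could not truthfully confirm taking product. Detailed instructions are deferred to a procedures manual that is not among the documents, and the consent pages were removed before review, so what participants would actually be told is unknown. The harm also needs several things to happen together, and the plan's powered endpoint tolerates a few early starters.

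Most of this stands. Intent is clear, an early start is unlikely to be common, and the loss is modest unless many do it. It does not remove the contradiction, and the safeguards have gaps. The Day 38 call comes 22 days after a possible early start. Table 1 lists calls only at Days 7, 38 and 45, so it is unclear whether the weekly calls run during washout. The container count shows how much was taken, not when: a participant who used everything on Days 16-29 returns empty containers and meets the 75% definition.

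**Conclusion.** The inconsistency is real. The start instruction is right for Visit 1 and wrong for Visit 2, and it should be corrected. It is a faulty dosing sentence in a plan whose intended schedule is otherwise clear. The washout is not missing, and the no-carryover assumption is not weakened.

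The size is conditional on the number of early starters, the supply dispensed and the effect remaining at Visit 3, none of which the plan gives. With up to 5 undetected early starters of 10, power on ATP/O2 stays at about 90% or more, but the expected effect falls by up to a quarter (0.50 to 0.375). The 65% figure requires all 10 to start early, undetected, with no effect left, and is an upper bound. The bias toward zero matters even where power holds. Correction is warranted because the sentence gives a wrong result if followed and costs almost nothing to put right.

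**What to change.** - In Section 5.0, limit the next-day start to product dispensed at Visit 1. State that product dispensed at Visit 2 must not be started until Day 38, at the Day 38 call, and put the same line on the Visit 2 participant instructions.
- At the Day 38 call, record whether any period 2 product has already been taken. If so, record a deviation and resupply a full 14 days before period 2 starts, or replace the participant under Section 4.3.
- Separately, and for consistency only, change the 4-week washout in Section 7.1 to 3 weeks. No effect of that discrepancy is claimed here.

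The first item alone removes the contradiction, and the second closes the detection and resupply gap. The cost is wording, one question at a call already planned, and product for anyone found to have started early. Visits, endpoints, analysis and sample size do not change.

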3.2 Exclusion Criteria

Criteria included in MEND:

- Pregnant
- Kidney transplantation
- Weight >400 lbs
- HIV infection
- End stage liver disease with cirrhosis
- Have physical immobility (defined by wheelchair use, oxygen-dependent COPD, shortness of breath after <100 steps)
- Have implants incompatible with MRI
- Institutionalization, or inability to consent
- Use medications interfering with muscle or mitochondrial function, including steroids, anti-psychotic, antivirals, muscle relaxants, oral calcineurin inhibitors, and anti-epileptic drugs
- Active malignancy
- Pacemaker
- Current participation in another interventional trial
- Non-English speaking

Additional Criteria:

- On chronic dialysis
- Expectation to start dialysis within 6 months or dialysis access in place.
- Insulin dependent diabetes
- Exercise limiting cardiopulmonary disease (e.g. angina, severe heart valve disease, severe COPD, coronary ischemia)
- Use of anticoagulation (i.e. warfarin)
- Baseline systolic blood pressure >170 or diastolic blood pressure >100
- Inflammatory conditions (e.g. autoimmune disease, HIV)
- Cirrhosis, active/chronic hepatitis
- Weight >300 lbs
- Personal history or family history of deep vein thrombosis, pulmonary embolism
- Patients hospitalized within the past 60 days for any reason.

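### No scheduled contact between Visit 2 (Day 15) and the period 2 start (Day 38) is described as asking about events, barred drugs or pregnancy, and the pregnancy-test schedule contradicts itself

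*Combined protocol and SAP*

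**What the plan says.** All references are to the combined protocol and SAP.

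**Contacts around the washout (section 5.0).** Product for period 2 is dispensed at Visit 2, Day 15. The washout is Days 16 to 37, and Table 1 marks nothing in that column. The Day 38 call is described as follows: "We will phone the subject to remind them to begin taking the treatment/placebo". At the visits on either side, the symptom questions read "At visit 2 the participant will be questioned regarding any concerning symptoms noted during the treatment period" and "During visit 3 the participant will be questioned regarding any concerning symptoms noted during the treatment period during visit 3". The Day 7 and Day 45 calls are made "to confirm patients are taking their treatment/placebo medication in order to ensure adherence", and to remind participants of visits.

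**Medications.** Section 4.6 lets participants keep taking their other drugs, "except those listed under criteria for exclusion or treatment discontinuation". Section 3.2 excludes people who "Use medications interfering with muscle or mitochondrial function, including steroids, anti-psychotic, antivirals, muscle relaxants, oral calcineurin inhibitors, and anti-epileptic drugs", and those on anticoagulants. Section 4.6 asks for drugs taken in the 4 weeks before enrolment. It adds that "Medications used for the treatment of AEs that occur during study participation also will be recorded", and has one incomplete sentence, with no time window, on recording prescribed and over-the-counter drugs. Table 1 marks the medication list at screening only.

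**Pregnancy.** Under section 4.5, a woman who becomes pregnant "will stop taking the study product, but will continue with study procedures with the exception of the MRS/OS procedures"; the reason given for omitting the scan is the unknown risk of ischemia. The section 5.0 text puts a urine test under the heading for Visits 1 to 3. Table 1 marks it at Visit 1 only, and the specimen table in section 9.2 counts one sample. The text and the Table 1 footnote also define differently who is tested: the footnote limits it to those who are sexually active.

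**The concern.** Two standing rules depend on information that someone has to collect: the bar on certain drugs and the stop rule for pregnancy. Followed literally, the schedule tells a participant to start the second product on Day 38 without a described question that would bring out an unreported event, a newly started barred drug or a pregnancy. For the placebo-first sequence this is the first glutamine exposure.

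The washout also follows a procedure with a stated hazard. Section 8.2 says that the 12-minute cuff inflation during the MR study raises the risk of thrombosis. For participants whose baseline scan comes from MEND, the first cuff inflation in this trial is at Visit 2. The weeks just after it are the ones that neither symptom question covers, and the cuff is applied again at Visit 3.

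At stake are participant safety, the completeness of adverse-event reporting (including the reports to the IRB on the first five completers, section 6.1), and knowing at Visit 3 whether a drug that acts on muscle or mitochondria was in use at the scan.

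**Working it through.** The plan gives no figure on this point, so the check compares the scheduled contacts and counts days from section 5.0 and Table 1. Section 7.1 speaks of a 4-week washout; the counts below use the day numbers of Table 1.

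| Contact | Day | What is described that bears on events, drugs or pregnancy |
|---|---|---|
| Screening | before Visit 1 | medical history, medication list |
| Visit 1 | -1 | pregnancy test (text and Table 1 agree) |
| Call | 7 | adherence, visit reminder |
| Visit 2 | 15 | symptoms in the treatment period; pregnancy test in the text, not in Table 1 |
| Washout | 16–37 | nothing marked |
| Call | 38 | reminder to start |
| Call | 45 | adherence, visit reminder |
| Visit 3 | 53 | symptoms in the treatment period; pregnancy test in the text, not in Table 1 |

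**Washout gap.**
- Length: 37 − 16 + 1 = 22 days.
- Visit 2 to period 2 start: 38 − 15 = 23 days.
- The next call comes 45 − 38 = 7 days after dosing starts and is about adherence.

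**Age of the medication list on Day 38.** It depends on when screening took place.
- Combined with Visit 1, which section 5.0 allows for some components: 38 − (−1) = 39 days.
- At the limit of the rule that Visit 1 follows within 28 days of screening (Day −29): 38 − (−29) = 67 days.
- At the start of Table 1's screening window (Day −90): 38 − (−90) = 128 days. This does not fit the 28-day rule, so 39 to 67 days is the safer range.

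No later review is marked in any column, so this gap runs through the whole study and not only the washout.

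**Pregnancy test, two readings.**

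| Interval | Table 1 and 9.2 (Visit 1 only) | Section 5.0 text (Visits 1–3) |
|---|---|---|
| Last test to Visit 2 MRS/OS | 15 − (−1) = 16 days | same visit |
| Last test to period 2 start | 38 − (−1) = 39 days | 38 − 15 = 23 days |
| Last test to Visit 3 MRS/OS | 53 − (−1) = 54 days | same visit |

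On both readings no test falls between Visit 2 and Day 38. A baseline scan repeated at Visit 1 would have a same-visit test on either reading.

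**People affected.** With 1:1 allocation of the 20 planned (section 7.3), 20 / 2 = 10 take their first glutamine on Day 38. With the maximum of 30 recruited (section 4.3), 30 / 2 = 15.

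**The case against.** The plan is not silent on safety in these weeks.
- Sexually active women of childbearing age are asked to use contraception throughout the study and for a month after (4.5).
- Participants can phone in adverse events, and staff document every event reported or observed, with no limit to the treatment period. A safety interview is mentioned without a date (6.2.1).
- The undated sentence in 4.6 may mean that new drugs are recorded throughout.
- The investigator can withdraw anyone for safety (3.6).
- Screening for thrombosis history is described for the MR study, timing not stated (8.2).
- Weekly calls (3.5) may run in the washout, and the procedures manual, which is not among the documents, may hold a call script.

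All of this stands as mitigation and keeps the point small. It does not close the gap. Phoning in depends on the participant, the weekly calls are described as covering adherence and reminders, and the rest schedules no question before Day 38.

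Some stronger readings are not supported. A reader might infer that the pregnancy rule has no scheduled check at all before period 2; the section 5.0 text supports a test on Day 15. A reader might infer that the medication gap belongs to the washout, or that later drugs go unrecorded; the first is study-wide, and on the second 4.6 is ambiguous. Nor do the documents require the entry criteria to be met again before period 2. Questions on Day 38 would serve the investigator's judgement.

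**Conclusion.** The point holds as a minor one, worth considering. Between Day 15 and Day 38 no scheduled contact is described as checking for events, barred drugs or pregnancy, and the 22 washout days stay outside the Visit 3 symptom question. Table 1 marks no medication review after screening. The pregnancy-test schedule is inconsistent; on the Table 1 reading the Visit 2 and Visit 3 scans come 16 and 54 days after the only test.

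This rests on reading the treatment period in the visit questions as the dosing days, on Table 1's day numbers, and on what the protocol itself schedules. A manual with a Day 38 script would answer part of it, but not the conflict over pregnancy tests. A reader might infer that participants will be dosed unsafely, or that the treatment comparison is biased or loses power. The documents give no event rates and nothing here supports either claim.

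**What to change.** 1. Make Table 1 and section 9.2 agree with the section 5.0 text: a urine pregnancy test at Visits 1, 2 and 3, before each MRS/OS, a sample count of 3, and one definition of who is tested.
2. On the existing Day 38 call, before telling the participant to start, ask about new health events, newly started drugs barred under 3.2 and 4.6, and possible pregnancy. Refer any yes to the investigator before dosing.
3. At Visit 3, before the MRS/OS, ask about symptoms, health changes and new medications since Visit 2, not only those in the treatment period. Ask about new medications at Visit 2 as well.

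**Cost.** A few minutes per contact and 3 − 1 = 2 more urine tests per eligible woman than Table 1 shows. If pregnancy is possible on Day 38, an occasional home test or unscheduled visit will be needed. A few period 2 starts will be delayed; Visit 3 should then move so that it stays 53 − 38 = 15 days after the start, the same interval as in period 1 (15 − 0 = 15). No additional participants are needed.
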